Evaluation of pharmacist interventions in lipid management for secondary prevention

NCT06647238

Document date: October 24, 2024

Lipids Research Protocol

Title: Second Time's the Charm: Evaluation of pharmacist interventions in lipid management for secondary prevention

Principal Investigator: [name], BCACP, CDCES, CPP

Co-Investigators:

[name], MSCR

[name], CDCES, BCPS, CPP, DPLA

[name], CDCES, BCPS, CPP

[name], PharmD

[name], BCACP, CDCES, CPP

[name], BCPS, CPP, CDCES

Background/Significance:

Studies have shown prevention of cardiovascular adverse events is directly proportional to percent reduction in LDL.¹ This evidence explains why LDL targets for secondary prevention have continued to be lowered. Cholesterol guidelines have been updated recently and encourage the use of multiple lipid lowering therapies, in addition to statins, for secondary prevention. However, these novel agents can be expensive and difficult to acquire, making prescribing challenging for providers.

This project aims to utilize a pharmacist to evaluate patients for evidence-based therapy and initiate guideline-directed lipid lowering therapy as indicated.

Study Purpose:

The primary objective of this research project is to compare the effect of pharmacist interventions versus usual care in the implementation of guideline directed lipid lowering therapies for secondary prevention.

Study Design: prospective interventional study

Methods/Data Collection

Patient Identification:

- Internal medicine providers and PharmDs will identify patients who are not meeting LDL goals for secondary prevention and could benefit from pharmacist intervention
- SlicerDicer will be utilized to select patients for the control arm as well as potentially for the intervention arm if referrals alone do not meet the sample size goal

Collected data will be stored on a secure Atrium server and de-identified. Data will be analyzed utilizing REDCap. Data collected via EPIC may include:

- Demographic information (age, gender, race)
- Baseline information (recent lipid panel, Lp(a) history)
- Initial hyperlipidemia treatment
- Relevant lab information (renal function, electrolyte values)
- Other co-morbidities (diabetes, CKD, etc)
- Insurance type
- Follow up appointments
- Other relevant patient information for an appropriate hyperlipidemia treatment recommendation

The study period is expected to be 5 months (anticipated November 2024-March 2025).

Inclusion Criteria:

- Age \geq 18 yo

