- Diagnosis of coronary artery disease
- Most recent LDL value > 55
- PCP at 1 of 6 identified clinics

Exclusion Criteria:

- Patients who are no longer an active patient of one of the internal medicine practices
- Patients whose cholesterol is managed by another practice
- Women of childbearing age/potential
- Patients residing in hospice/LTC facilities
- End-stage liver disease

Practice Sites:

- Kannapolis Internal Medicine
- Concord Internal Medicine
- Ardsley Internal Medicine – Harrisburg

- Atrium Health Primary Care Cabarrus Family Medicine – Locust
- Atrium Health Primary Care Cabarrus Family Medicine - Midland

In-person, initial visit:

- Perform medication reconciliation and adherence assessment
- Assess recent laps in EPIC profile
- Educate patient on background of project (pharmacist lipid intervention), provide information sheet, future steps/plans
- Adjust hyperlipidemia treatment, which is part of the routine clinical practice under the collaborative practice agreement.
 - CPP is a licensure that is obtained from the NC Board of Pharmacy and is renewed yearly; CPPs must complete an additional 20 hours of continuing education each year
 - A CPP has an established collaborative practice agreement (CPA) with a supervising physician that outlines the role of the CPP
 - Each pharmacist working on this project either practice as a CPP or are under the direct supervision of CPP
- Order appropriate lab work
- Arrange follow-up with patient regarding medication changes (phone visit)
 - Follow up visits will be scheduled every 6-8 weeks as needed based on patient-specific needs
 - Once LDL<55 (controlled), no further follow up will be scheduled with PharmD
- Will also plan to check Lp(a) for patients who have never had this lab assessed
 - Will provide information sheet on this lab and what to do if it comes back as elevated

Follow up visits:

- Repeat lipid panel prior to appointment, review results
- Assess adherence and access to recommended therapy
- Discuss therapy adjustments
- Set up next follow up visits

The initial in-person visit, or a follow-up telephonic phone visit may be completed by another embedded pharmacist within one of the clinics included in study due to schedule availability. Members of the PharmD team will be trained and follow the protocol during their visits.

Medications are being adjusted as per the usual care services provided by their PCP office and

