PharmD services that are already in place at each practice. Adjustments to medication regimens, comorbidities, and concurrent medications will be made based on national guidelines and evidence-based recommendations that are already allowable by CPP and per our collaborative practice agreement. Any costs/risk associated with medication changes is no additional risk than if they do not participate in the study and would still be subject to these medication changes if they weren't participating in the study. This study and applicable additional intervention are simply offering additional care services provided by a PharmD for closer follow up and offering patients assistance with access to newer therapeutic options.

Control Group:

Patients meeting inclusion criteria will be pulled from SlicerDicer. Any patients previously referred to the project by their provider will be excluded from the control group. Patients included in the report will then be randomized and chosen for retrospective chart review. The goal will be to include 75 patients in both the intervention and control arms. Investigators will perform retrospective chart review for the study period and record the same data as collected for patients in the intervention arm.

Primary endpoint: patients with LDL within goal (<55) (yes/no)

Secondary endpoints:

- Percent LDL reduction (will use baseline LDL and lowest LDL)
- Medication related problems identified and solved
- Medications initiated or titrated
- Number of patients who were provided assistance with access to medication
- Prevalence of elevated Lp(a)

Data and Safety Monitoring:

Principal investigator and co-investigators will meet monthly to re-evaluate patient enrollment and ensure all investigators are adhering to study protocol.

Statistical Analysis:

Data will be analyzed after de-identification using descriptive statistics or inferential statistics as appropriate and will be collected, organized, and stored through REDcap. T-test will be utilized to compare pharmacist intervention versus usual care on the primary outcome. Descriptive statistics will be utilized to report secondary outcomes.

Feasibility of Project:

The anticipated start date for patient enrollment is November 2024. Statistical analysis will be finalized by April 2025. Anticipate presentations/publication in May or June 2025.

Informed Consent:

Participants will be required to provide signed informed consent prior to inclusion in the study.

References:

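### Percent LDL reduction is measured to each patient's lowest LDL, so the arm tested more often looks better with no true difference; the primary endpoint can carry the same bias

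*Combined protocol and SAP*

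**What the plan says.** Under Secondary endpoints, the second LDL outcome is "Percent LDL reduction (will use baseline LDL and lowest LDL". No time point, window or number of tests is attached to it.

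The two arms get their LDL values differently.

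- **Intervention arm.** The section on the initial visit states "Follow up visits will be scheduled every 6-8 weeks as needed based on patient-specific needs". The section on follow-up visits adds "Repeat lipid panel prior to appointment, review results". Pharmacist follow-up then has an outcome-dependent end: "Once LDL<55 (controlled), no further follow up will be scheduled with PharmD".
- **Control arm.** Under Control Group: "Investigators will perform retrospective chart review for the study period and record the same data as collected for patients in the intervention arm". This fixes which items are abstracted, not how often LDL is measured.

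Entry in both arms requires "Most recent LDL value > 55". On timing, Methods/Data Collection states "The study period is expected to be 5 months (anticipated November 2024-March 2025".

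The primary endpoint is a yes/no for LDL below 55. It does not say which LDL counts or when, or how a patient with no follow-up LDL is classed. Under Statistical Analysis, the primary outcome is compared by t-test and the secondary outcomes are described only.

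**The concern.** A single LDL reading varies around the patient's true level. The minimum of two readings is lower on average than one reading, even if nothing has changed. An endpoint built on the minimum therefore rewards the arm with more readings, and the plan neither equalises nor adjusts for the number of readings.

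If intervention patients are tested more often, part of their reported reduction is a product of measurement. More patients would not remove it. Gains from closer follow-up and titration are real effect and are not in question.

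The primary endpoint is exposed because the counting LDL is not named. If any value below 55 qualifies, extra tests are extra chances to cross the line by luck. If the last value qualifies, much the same can happen. Pharmacist follow-up ends at the first value below 55, so a chance low reading stays the last one unless usual care draws another. That last step is an inference from the text.

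**Working it through.** The plan gives no figure to reproduce on this point. The check asks how large the artefact is when true LDL does not differ between arms.

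**Inputs from the documents:** entry LDL above 55; panels every 6-8 weeks; pharmacist follow-up ends at the first LDL below 55; 5-month study; 75 per arm.

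**Assumed, not in the documents:** within-person CV 7-10%; true LDL mean 75-90, SD 25; one follow-up test per control; enrolment uniform over the first 13 weeks of 21.5.

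**Step 1: panels per intervention patient.** Remaining follow-up runs uniformly from 21.5 − 13 = 8.5 to 21.5 weeks. At 7-week spacing:
- one panel: (14 − 8.5)/13 = 42.3%
- two panels: (21 − 14)/13 = 53.8%
- three panels: (21.5 − 21)/13 = 3.8%

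**Step 2: drop in the minimum.** With reading = true × (1 + CV × Z) and Z standard normal, the expected minimum lies below the true value by 0 for one reading, CV/√π = 0.564 × CV for two, and 3 × CV/(2√π) = 0.846 × CV for three.

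**Step 3: excess percent reduction, no true change.**
- CV 7%: 0.538 × 0.564 × 7 + 0.038 × 0.846 × 7 = 2.12 + 0.23 = 2.35 points
- CV 10%: 0.538 × 0.564 × 10 + 0.038 × 0.846 × 10 = 3.03 + 0.32 = 3.36 points (from unrounded terms)

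Simulation that adds the entry threshold and the stop below 55 gives 2.3-3.4. At 8-week spacing it gives 1.7-2.4, and at 6-week spacing 3.4-4.9.

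**Step 4: dependence on control testing** (7-week spacing, no true change, simulated).

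| Control tests | Intervention excess, points |
|---|---|
| One each | 2.3 to 3.4 |
| Half have two | 0.4 to 0.5 |
| Same number as intervention | about 0 |
| All have two | −2.3 to −1.6 |

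**Step 5: if treatment works** (assumed effects, one control test). With a true 30% fall by the first panel and no more, the artefact is about 1-2 points. With a further 15-25% fall at each later adjustment it is 0.3-0.7 points, on a reduction of about 33-37%. Later readings are then truly lower, and fewer patients reach a second panel: 28-39% instead of 54-57%.

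**Step 6: primary endpoint, no true change.** If any LDL below 55 counts, the attainment excess is 0.5-2.4 points at 7-week spacing. That is 75 × 0.005 = 0.4 to 75 × 0.024 = 1.8 patients. At 6-week spacing it reaches 3.5 points (75 × 0.035 = 2.6 patients). If the last LDL counts and 25%, 50% or 100% of intervention patients have a later usual-care LDL, the excess is 0.4-1.7, 0.3-1.1 or about 0. With no later usual-care LDL, it equals the any-LDL excess.

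**Step 7: alternative rules, no true change.** Taking the last LDL cuts the percent-reduction artefact to about 0.1-0.4 points. It is not exactly zero because follow-up stops on a low reading. Taking the first LDL brings both artefacts to about 0.

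**The case against.** **The direction is not established.** Visits are as needed, and the protocol describes pharmacist services as already in place at each practice, so controls may be retested too. This stands. A reader might infer that the plan is biased in favour of the pharmacist arm. The documents support only that it favours whichever arm is tested more, and Step 4 shows the sign can change.

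**The no-change figures overstate the distortion if the intervention works.** This also stands for percent reduction (Step 5). The 2.3-3.4 points matter most for a false claim of benefit. The shrinkage does not carry over to goal attainment, where misclassification near 55 persists.

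**The weight is modest.** Percent reduction is secondary and untested. A reader might go further and assume three panels for every intervention patient against one per control, and infer serious type I error inflation on the primary test. The documents do not support that: visits are as needed, enrolment is staggered and follow-up ends below 55. On the timeline above only about 4% reach three panels. Likewise, any excess from classing untested controls as failures is a missing-data problem, not an effect of the lowest-LDL rule.

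**More testing is part of the intervention.** Its effect on treatment is. The excess in Steps 3 and 6 arises with true LDL unchanged.

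**Conclusion.** The concern holds in conditional form. The lowest-LDL rule makes the result depend on how often each arm is tested, and only the intervention arm has scheduled panels. The mechanism follows from the definition. The sign depends on control testing, which the documents do not give, and the size rests on the assumed CV, LDL distribution, visit spacing and enrolment pattern, so it is of low certainty.

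On those assumptions the percent-reduction artefact runs from a few points with no true change to under 1 point with continuing titration. For the primary endpoint it amounts to fewer than 2 of 75 patients at 7-week spacing if any LDL counts. This is a modest, systematic bias. It should be fixed because the remedy is cheap and the primary endpoint needs a named LDL in any case. It is not grounds for calling the primary comparison invalid.

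**What to change.** Replace the lowest LDL with one LDL per patient, chosen without regard to its value and by the same rule in both arms, and use it for both LDL endpoints:

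- **Endpoint LDL:** the last LDL after the index date and within the study period.
- **Index date:** the initial pharmacist visit; for controls, a date assigned before follow-up LDLs are viewed.
- **Baseline:** the last LDL on or before the index date.
- **Reporting:** the number of LDL tests and the number of patients without a follow-up LDL, by arm, with a stated rule for the latter.
- **Supportive only:** lowest LDL and ever below 55.
- **Optional sensitivity analysis:** the first LDL in a common window such as weeks 4-12, because the last-LDL rule can leave some excess in attainment. Opening at week 4 keeps panels drawn ahead of a 6-week visit and excludes early results from the initial-visit instruction "Order appropriate lab work".

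The first-LDL window is better kept as a sensitivity analysis. It reflects mainly the first adjustment and loses controls. If usual care draws LDL at random once per 13 to 52 weeks (assumed), weeks 4-12 capture 44% down to 14% of controls. The last-LDL rule captures 1 − (m/13) × (e^(−8.5/m) − e^(−21.5/m)) for mean interval m weeks: 67% at m = 13 and 25% at m = 52. For an assumed 40% against 20% attainment with 75 intervention patients (normal approximation, two-sided 5%), power is about 30-61% with the window (10-33 controls). With the last LDL (19-50 controls) it is about 46-71%: z = 0.20/√(0.24/75 + 0.16/n) − 1.96 = −0.10 at n = 19 and 0.54 at n = 50.

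The cost is a short paragraph, a slightly smaller reported reduction, and a small residual attainment bias. No visits or tests are added and clinical follow-up is unchanged. The rule should be fixed before follow-up LDLs are viewed.

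### The primary endpoint is compared between non-randomised arms by a t-test without covariates; a model adjusted for baseline LDL and lipid therapy, with common baseline and outcome rules, is better at small cost.

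*Combined protocol and SAP*

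**What the plan says.** **Test.** Under Statistical Analysis: "T-test will be utilized to compare pharmacist intervention versus usual care on the primary outcome". The same section allows descriptive or inferential methods where suitable, but names no other primary method and no covariate.

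**Intervention arm.** Under Patient Identification: "Internal medicine providers and PharmDs will identify patients who are not meeting LDL goals for secondary prevention and could benefit from pharmacist intervention". The electronic-record query tool may also be used, "potentially for the intervention arm if referrals alone do not meet the sample size goal". The share expected from that route is not given.

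**Control arm.** Under Control Group, charts come from the same tool, and "Any patients previously referred to the project by their provider will be excluded from the control group". Charts are then picked at random. The word randomized there describes which charts are drawn, not who receives the intervention.

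**Entry level.** "Most recent LDL value > 55", with no upper limit.

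**Covariate data.** The data list opens with "Data collected via EPIC may include" and contains a recent lipid panel and "Initial hyperlipidemia treatment". Controls are to have the same data recorded. Baseline LDL is also needed for the percent-reduction secondary endpoint. Starting therapy is in effect needed for the secondary endpoint on drugs started or dose-adjusted. Secondary endpoints are reported descriptively.

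**Follow-up LDL.** Intervention visits specify "Repeat lipid panel prior to appointment, review results". Controls have chart review only. No outcome window and no rule for a missing follow-up LDL is given.

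**The concern.** A patient who starts at 60 and one who starts at 140 both qualify, and both are scored only on whether they end below 55. Their distances to goal are very different. What therapy remains to be added also affects the chance of getting there. The arms are formed by different routes, so nothing in the design makes these two factors comparable, and the only named primary test uses neither.

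If they differ between arms, the t-test can show a difference when there is none or hide a real one. If they happen to be balanced, the test keeps its error rate but gives up power that data already on the collection list could supply.

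**Working it through.** **Inputs from the documents.** Goal of 75 per arm; binary endpoint; LDL above 55 at entry; no random allocation. Alpha, power, expected goal rates and effect size are not stated, so the figure of 75 cannot be reproduced. At an assumed two-sided 5% and 80% power, 75 per arm detects differences of 15.1 to 22.4 points for control goal rates of 5% to 30%.

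**Step 1: is a t-test on yes/no data itself the fault?** No. Simulated false rejection at 75 per arm, for goal rates of 5-30%, is 4.7-5.0%, the same as chi-square.

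**Step 2: no effect, baseline LDL unequal.** Two outcome models were simulated, every input assumed, with 2,000-3,000 trials per case in the main runs. Near 5%, the Monte Carlo standard error with 2,000 trials is √(0.05×0.95/2000) = 0.5 points.

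*Model A.* Baseline LDL is lognormal, truncated above 55. Follow-up LDL = baseline × 0.70 if intensified (40% in both arms) × lognormal noise (SD 0.15 or 0.22). The adjusted analysis is the logistic Wald test with log baseline LDL. Unless stated, log SD is 0.30.

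| Baseline LDL, intervention vs control | t-test rejects | Adjusted rejects |
|---|---|---|
| balanced | 5.1% | 4.3-5.0% |
| 95 vs 90 | 8.2-8.9% | 4.6-5.2% |
| 100 vs 90 (log SD 0.20-0.35) | 13.8-23.4% | 3.8-5.2% |
| 90 vs 100 | 16.9-17.2% | 4.4-5.2% |

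The spurious gap is about -6 points at 100 vs 90 and about +6 points at 90 vs 100.

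*Model B.* Control mean LDL 90, control goal rate about 26%, log-odds of goal -0.04 per mg/dL of baseline LDL and -0.7 for intensive baseline therapy. The adjusted analysis is the standardised risk difference with a delta-method standard error.

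| Intervention arm relative to control | t-test bias | t-test rejects | Adjusted rejects |
|---|---|---|---|
| balanced | +0.2 points | 5.5% | 5.8% |
| LDL +10 | -4.1 | 10.3% | 5.9% |
| LDL +20, intensive therapy +15 points | -9.0 | 27.9% | 6.2% |
| LDL -15, intensive therapy -15 points | +11.4 | 32.3% | 6.3% |

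Hand check: with bias b and standard deviation s of the crude difference, P(reject) ≈ Φ(b/s - 1.96) + Φ(-b/s - 1.96).
- Second row: 0.041/0.0715 = 0.573, giving 8.8%.
- Third row: 0.090/0.0681 = 1.322, giving 26.2%.
- Fourth row: 0.114/0.0767 = 1.486, giving 31.8%.

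These are close to the simulated values. The risk difference runs at about 6%, slightly above the Wald test.

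**Step 3: real effect, balanced arms.**
- Model A (75% vs 30% intensified): power 51.1-60.1% unadjusted, 62.2-76.7% adjusted, a gain of 11.1 to 16.6 points.
- Model B (about +23 points): 84.4% to 91.3%, a gain of 6.9 points.
- Repeat runs of Model A gave gains of up to about 20 points.

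**Step 4: therapy mix also differs.** Model A, LDL 100 vs 90, no effect. Therapy none / statin only / any non-statin is 10/65/25% vs 30/60/10%, and the LDL factor if intensified is 0.60/0.72/0.80. Rejection is 25.5-28.5% for the t-test, 6.6-7.0% with LDL only, and 5.2-5.3% with LDL and therapy. With about 23-27 events, the three-level therapy term was not estimable in 4-10% of fits. After merging to none vs any, this fell to 0-0.2%.

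**Step 5: what adjustment cannot repair.** Model A, no pharmacist effect. In the retesting rows, untested controls count as not at goal.

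| Case | t-test rejects | Adjusted rejects |
|---|---|---|
| 80% of controls retested, LDL balanced | 9.6-10.7% | 10.6-11.0% |
| 60% retested, LDL balanced | 25.3-27.7% | 28.5-31.7% |
| engagement alone: 60% vs 40% intensified | 13.7-17.3% | 17.5-21.0% |
| 60% retested and LDL 100 vs 90 | about 6-8% | about 21-27% |

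Hand check of the testing effect: a true 20% in both arms appears as 20% vs 0.20×0.60 = 12%. The standard error is √(0.20×0.80/75 + 0.12×0.88/75) = 0.0595, the ratio 0.08/0.0595 = 1.344, and rejection about 27%.

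In the last row of the table the t-test looks sound only because a bias against the intervention offsets a bias in its favour. Removing one exposes the other.

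**The case against.** The strongest counter-argument is the last row of Step 5. Intervention patients have scheduled repeat panels and controls do not, so unequal testing is plausible here. In that setting the adjusted model alone can raise false positives from about 6-8% to about 21-27%. This stands. It does not rescue the t-test, whose low rate there is an accident of cancellation, but it means that adjustment must come with a common outcome window and a missing-LDL rule.

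The figures also depend on invented inputs. For the same 10 mg/dL gap one model gives about 10% and the other up to 23%. This stands too, and they carry weight only as illustration.

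The general wording on suitable inferential methods would permit an adjusted analysis. It does permit one, but it pre-specifies none.

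Three stronger readings are tempting and are not supported:
- **The planned result will be biased in a particular direction.** The documents give no LDL distribution and no referral threshold, and the imbalance could run either way.
- **A t-test on a yes/no endpoint is invalid.** Step 1 shows it keeps its error rate at this size when the arms are comparable.
- **Baseline therapy plays no part in the planned outcomes.** The secondary endpoint on drugs started or titrated in effect needs it, and medication reconciliation is part of the initial visit.

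**Conclusion.** The point holds as a low-cost improvement. The plan leaves a very likely strong predictor, which it must already hold for every patient, out of the only primary test between arms that are not randomly allocated.

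Under assumed inputs, a 10 mg/dL baseline difference with no effect takes the t-test to about 10-23% false rejection, against about 4-6% adjusted (about 6% for the risk difference recommended below). With balanced arms and a real effect, the gain is roughly 7-20 points of power. The low adjusted rates assume equal outcome ascertainment and no unmeasured confounding.

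A reader might infer that adjustment makes the comparison as good as randomised. It does not: referrer judgement, engagement, consent and unequal follow-up testing remain.

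**What to change.** Make the primary analysis a logistic regression of LDL below 55 on arm, log baseline LDL and baseline lipid therapy. State in advance that therapy levels without events are merged (for example none vs any) or that a penalised fit is used. Report the standardised risk difference with a 95% CI, keep the unadjusted comparison as supportive, and tabulate baseline LDL and therapy by arm.

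As part of the same change, and not as an option:
- assign an index date to every patient, controls included, and define baseline LDL from it in the same way in both arms (for example the last value before that date);
- set one outcome window for both arms and a stated rule for a missing follow-up LDL;
- commit to recording baseline therapy in both arms;
- describe the result as a non-randomised association.

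**Cost.** SAP wording and one short model; the goal of 75 per arm is unchanged. Baseline LDL must already exist for eligibility. The downsides are a slightly more complex primary analysis, a sparse-level rule, and the work of assigning an index date to controls.

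### The plan names a t-test, with no version or effect measure, for a yes/no primary endpoint; this is harmless at 75 vs 75 but leaves the result open if evaluable numbers become unequal

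*Combined protocol and SAP*

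**What the plan says.** The endpoint is binary: "Primary endpoint: patients with LDL within goal (<55) (yes/no". The only sentence on its analysis, under Statistical Analysis, is "T-test will be utilized to compare pharmacist intervention versus usual care on the primary outcome". The sentence before it is general: "Data will be analyzed after de-identification using descriptive statistics or inferential statistics as appropriate". The plan does not state pooled or Welch, alpha, sidedness, an effect measure or a confidence interval.

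On numbers, the Control Group section says "The goal will be to include 75 patients in both the intervention and control arms". No rates, effect size or power accompany the 75.

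Outcomes reach the two arms by different routes. Under Follow up visits, intervention patients have a lipid panel before each appointment ("Repeat lipid panel prior to appointment, review results"). For controls, "Investigators will perform retrospective chart review for the study period and record the same data as collected for patients in the intervention arm". No control panel is scheduled, and no rule covers a patient without a follow-up LDL.

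**The concern.** A t-test compares means, and this endpoint is a proportion. The two usual versions estimate the standard error differently. With equal arms the two standard errors are the same; with unequal arms they are not. A report could then be significant or not depending on a software default or on a choice made after seeing the data. Any interval that comes with the test could also be too wide or too narrow. Because no effect measure is named, the plan does not commit to reporting the difference in proportions at all.

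**Working it through.** **Inputs.** From the documents: a binary endpoint, a t-test of unstated version, and a goal of 75 per arm. Assumed, because the documents are silent: two-sided 5%; evaluable numbers from 75/75 to 75/25 and the reverse down to 38/75 (intervention/control); 5-50% at goal under the null; 30% vs 5% or 30% vs 10% where the arms differ. The 75 cannot be reproduced, since no inputs for it are given.

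**Step 1: pooled t and chi-square are nearly the same test.** With N patients in total, t² = χ²(N − 2)/(N − χ²) for 0/1 data, at any allocation. Example, 30/75 vs 15/75: χ² = 0.20²/(0.3 × 0.7 × 2/75) = 7.143, so t² = 7.143 × 148/142.857 = 7.40 and t = 2.72. The p-values are 0.0073 (pooled t) and 0.0075 (chi-square). For 30/75 vs 10/50 they are 0.0187 and 0.0189; Welch gives 0.0146.

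**Step 2: type I error.** Every pair of binomial counts was enumerated and the probabilities of the rejecting tables were summed.

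| Evaluable | At goal, both arms | Pooled t | Chi-square | Welch |
|---|---|---|---|---|
| 75/75 | 5% | 4.9% | 4.9% | 4.2% |
| 75/75 | 10% | 5.1% | 5.1% | 4.8% |
| 75/50 | 5% | 4.4% | 4.4% | 5.8% |
| 75/50 | 10% | 5.7% | 5.7% | 5.2% |
| 75/50 | 20% | 5.5% | 5.5% | 4.7% |
| 75/35 | 5% | 3.3% | 3.3% | 9.4% |
| 75/25 | 5% | 3.3% | 3.3% | 14.7% |
| 75/25 | 10% | 4.1% | 4.1% | 9.0% |

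At 75/35 Welch falls back to 5.7% with 10% at goal and 5.4% with 20%.

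**Step 3: one data set, two answers.** Take 15/75 vs 2/35, a difference of 0.200 − 0.057 = 0.143.
- The sample variances are 75 × 0.2 × 0.8/74 = 0.1622 and 35 × 0.0571 × 0.9429/34 = 0.0555.
- Pooled: variance (74 × 0.1622 + 34 × 0.0555)/108 = 0.1286; SE = √[0.1286 × (1/75 + 1/35)] = 0.0734; t = 1.95; p = 0.054.
- Welch: SE = √(0.1622/75 + 0.0555/35) = 0.0612; t = 2.33; p = 0.022.
- Chi-square: p = 0.054.

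With true rates of 30% vs 10%, Welch and chi-square disagree at 0.05 in 8.2% of trials at 75/35 and 13.6% at 75/25. With 30% vs 5% they disagree in 0.4% at 75/50 and 3.7% at 75/35.

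**Step 4: interval, if one is reported.** The pooled SE assumes equal variances, which fails when the rates differ. For 30% vs 5% the variances are 0.3 × 0.7 = 0.21 and 0.05 × 0.95 = 0.0475.
- At 75/35 the true variance of the difference is 0.21/75 + 0.0475/35 = 0.00416. The pooled one averages (74 × 0.21 + 34 × 0.0475)/108 × (1/75 + 1/35) = 0.00666. The SE ratio is √(0.00666/0.00416) ≈ 1.27, so the interval is too wide.
- At 38/75 they are 0.21/38 + 0.0475/75 = 0.00616 and (37 × 0.21 + 74 × 0.0475)/111 × (1/38 + 1/75) = 0.00403. The ratio is about 0.81, so the interval is too narrow.

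Exact coverage of nominal 95% intervals, 30% vs 5%:

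| Evaluable | Pooled t | Newcombe |
|---|---|---|
| 75/35 | 98.6% | 95.8% |
| 75/25 | 99.3% | 96.5% |
| 50/75 | 90.5% | 95.1% |
| 38/75 | 88.2% | 95.3% |

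At 75/75 pooled-t coverage is 95.0%. Miettinen-Nurminen coverage was not enumerated.

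**The case against.** The case for leaving the plan alone is substantial.

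- The goal is 75 in both arms, and there the choice of test makes no practical difference. This stands.
- Unequal numbers are an inference. Further control charts could be drawn from the same report, and if a patient with no recorded LDL below 55 counts as not at goal, the denominators stay at 75/75. This stands as far as it goes, but the plan states neither a replacement rule nor a counting rule. The reverse imbalance is possible too, since the Patient Identification section foresees that referrals alone may not reach the sample size goal.
- The large Welch figures need three things together: software that runs Welch, 53-67% of controls without an evaluable LDL (40/75 and 50/75), and 5% at goal in both arms. About 94% of the Welch rejections at 75/35 and 98% at 75/25 come from tables with nobody at goal in one arm. This stands, and it limits the point to a corner.
- No interval is planned, and with fewer controls and a lower control rate the pooled interval is conservative. Both are true. Under-coverage arises when the intervention arm is the smaller one and has the higher rate.
- The clause allowing statistics as appropriate gives some latitude, but it does not override the specific t-test sentence that follows it.

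A reader might infer that a t-test on a yes/no outcome gives a wrong p-value as soon as the arms are unequal, and that inequality is likely here. Neither is supported. The pooled t tracks chi-square at every allocation tried, disagreeing in at most about 1.3% of trials, and the documents give no missing-LDL rate from which to judge likelihood.

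**Conclusion.** The mismatch between test and endpoint is certain, and so is the absence of a version and an effect measure. The numerical consequence is conditional. It is negligible at 75 vs 75 with complete data, and for the pooled p-value at any allocation. It is material for Welch only with low rates and marked imbalance (9.4% and 14.7% at 5% at goal, against 4.7-5.8% at 75/50). It is material for a pooled-t interval only when sizes and rates both differ (98.6% or 88.2% coverage for 30% vs 5%). All of these rest on assumed evaluable numbers, rates and a two-sided 5% level. The point is minor, because the conclusion would seldom change from the choice of test alone.

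**What to change.** Replace the t-test sentence in Statistical Analysis with: the proportion of patients at goal will be reported for each arm, with the difference in proportions and a Newcombe (or Miettinen-Nurminen) 95% CI; the arms will be compared by a two-sided Pearson chi-square test, or an exact test if any expected count is below 5. The sponsor should name one interval method in advance. The exact-test fallback would apply where Welch misbehaves most: 5% of 35 or 25 controls is an expected 1.75 or 1.25 at goal.

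The cost is one sentence and no new data. It does not settle how patients without a follow-up LDL are counted. That is a separate gap and needs its own rule, because a chi-square test on selectively evaluable patients would carry the same selection problem.
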